4. CHANGES IN THE PLANNED ANALYSIS OF THE STUDY

In writing the core TSAP, these corrections were made to the specifications of the initial TSAP:

1. Important protocol deviation (IPD) E1 in Section 6.2 “No post-baseline 6 MWT assessments” was clarified to E1 “No post-baseline 6 MWD assessments at 12 weeks” and E2 “No baseline 6 MWD assessments” to reflect the primary outcome being measured at 12 week visit.
2. iPD D2 in Section 6.2 was changed from “Discontinued nintedanib” to “Discontinued nintedanib before 12 week visit” to reflect the primary outcome being measured at 12 week visit.
3. The Screening trial period in Section 6.1 was changed from “informed consent to randomization” to “first informed consent to randomization” to account for re-consenting of patients.
4. The trial periods defined in Section 6.1 was clarified to make the distinction between efficacy analysis and safety analysis.

Following termination of the trial, limited efficacy analysis will be performed for an abbreviated CTR. Primary and secondary endpoints will be limited to descriptive outcome measures. Further endpoints will not be done.

5. ENDPOINTS

5.1 PRIMARY ENDPOINT

The primary endpoint is the change from baseline in Six-Minute Walk Test (6MWT) distance at 12 weeks.

5.2 SECONDARY ENDPOINTS

5.2.1 Key secondary endpoints

There are no key secondary endpoints defined for this trial.

[figure not shown]
5.2.2 Secondary endpoints

[figure not shown]
The secondary endpoints are:

[figure not shown]
- Change from baseline in Quality of Life (QoL) (SGRQ, KBILD, UCSD-SOBQ) at 12 and 24 weeks
- Change from baseline in 6MWT distance at 24 weeks
- Change from baseline in Forced Vital Capacity (FVC) at 12 weeks and 24 weeks using each of
 - Absolute change from baseline of FVC and FVC % predicted
 - Relative change from baseline of FVC and FVC % predicted
 - Absolute categorical change of FVC % predicted (decrease by >5%, increase by >5%, and change within ≤ 5%)

- Absolute categorical change of FVC% predicted (decrease by >10%, increase by >10%, and change within $\leq 10\%$)
- Change from baseline in daily accelerometer activity from baseline at 12 and 24 weeks
 - Score of average Steps/day
 - Score of average VMU/day

Refer to Section 6.7 for baseline value definition. Refer to Section 6.6 for missing baseline assessment.

6. GENERAL ANALYSIS DEFINITIONS

6.1 TREATMENT(S)

For treatment specifications, see Section 4 of the CTP.

The following trial periods will be defined with respect to efficacy analyses: Screening, Post-randomization, Treatment, Post-treatment.

- Screening: from first informed consent to randomization
- Post-randomization: from randomization to day of first pulmonary rehabilitation (for those randomized to Pulmonary Rehabilitation Treatment group)
- Treatment:
 - For patients randomized to the Non-Pulmonary Rehabilitation Treatment group: from randomization to the visit 7 end-of-trial visit
 - For patients randomized to the Pulmonary Rehabilitation Treatment group: from first day of pulmonary rehabilitation to the visit 7 end-of-trial visit
- Post-treatment: after the visit 7 end-of-trial visit

Efficacy analyses is independent of nintedanib usage: any dose interruption or discontinuation has no effect on the efficacy analyses. Efficacy analyses will be done on the Post-randomization and Treatment Periods.

The following trial periods will be defined with respect to safety analyses:

Note: the last day of each of the following periods is excluded.

- Screening: from first informed consent to randomization
- Post-randomization: from randomization to day of first Nintedanib drug intake on/after randomization. This period only exists if Nintedanib first drug intake on/after randomization occurred at least 1 day after randomization.
- Treatment: from first Nintedanib drug intake on/after randomization (or re-start of nintedanib if interruption) to last Nintedanib drug intake (or the day before start date of interruption if interruption) plus one day.
- Off-treatment^a: From the start date of Nintedanib interruption to re-start of Nintedanib treatment.
- Residual-effect^a: From the last Nintedanib drug intake plus one day to last Nintedanib trial drug intake plus 28 days plus one day.
- Post-treatment^a: From last trial drug intake plus 29 days. Note, this period is only created if last Nintedanib intake plus 29 days took place before trial completion.
- Post-study: from the latest of last trial drug intake plus 29 days or date of trial completion plus 1 day

^a Note: This period is optional insofar as it does not necessarily exist for all patients.

6.2 IMPORTANT PROTOCOL DEVIATIONS

The following table defines the different categories of important protocol deviations (IPD) to be considered. Important efficacy IPDs are those that can potentially influence the primary endpoint. No patients will be excluded from the analyses based on those IPDs as no per-protocol analysis is planned. However, the frequency of patients with IPDs will be presented.

Table 6.2: 1 Important protocol deviations

Category / Code	Description	Requirements
A	Entrance criteria not met	
A1	Inclusion criteria not met	Inclusion criteria not met as specified in the protocol. Automatic PD
A2	Exclusion criteria not met	Exclusion criteria not met as specified in the protocol. Automatic PD
B	Informed consent	
B1	Informed consent not available/not done	Informed consent date missing Automatic PD
B2	Informed consent too late	CRF date of informed consent Automatic PD
B3	Informed re-consent not available/not done	Informed re-consent date missing Manual PD
B4	Informed re-consent too late	CRF date of informed re-consent Manual PD
B5	Incorrect consent form used or other consenting process error	Manual PD
C	Trial treatment and randomisation	
C1	Incorrect treatment given	Patient assigned to pulmonary rehabilitation not prescribed rehab, or patient assigned to standard care prescribed rehab Manual PD with medical review of MQRM listings
C2	Non-compliance	Pulmonary Rehabilitation Compliance <80% or >120% Automatic PD with medical review of MQRM listings
D	Concomitant medication	
D1	Patient received prohibited concomitant therapies during treatment phase	Manual PD with medical review of MQRM listings
D2	Mandatory medication not taken	Discontinued nintedanib before 12 week visit Automatic PD
E	Missing data	
E1	No post-baseline 6 MWD assessments at 12 weeks	Automatic PD
E2	No baseline 6 MWD assessments	Automatic PD

[figure not shown]
Automatic PDs are those detected via an automatic programming process using SAS. Manual PDs are those identified during the MQRM meeting through patient listings and/or BI CTMS.

6.3 SUBJECT SETS ANALYSED

- Screened set
This patient set includes all patients having signed informed consent and performed visit 1.
- Randomized set (RS)
This patient set includes all randomized patients, whether treated with pulmonary rehabilitation or not

- [REDACTED]

All analyses will be done on the RS or [REDACTED]. Note that the number of patients with available data for an endpoint may differ. For details, see Section 6.6.

6.5 POOLING OF CENTRES

This section is not applicable because centre/country is not included in the statistical model.

6.6 HANDLING OF MISSING DATA AND OUTLIERS

In general, the efficacy analyses as well as safety analyses will be evaluated by observed case analysis (OC), i.e. using only available data without imputation.

6.6.1 Primary Endpoint

~~Multiple imputation will be used to handle missing data as a sensitivity analysis for the primary endpoint. Further detail is provided in Section 7.4.2.~~

6.6.2 Secondary Endpoints

6.6.2.1 Saint George's Respiratory Questionnaire

For the SGRQ, the SGRQ manual (7) allows for 25% of missing data per component (i.e., 2

questions for symptoms, 6 questions for impacts and 4 questions for activities). The rules defined in the SGRQ manual will be used to derive the SGRQ.

Additionally the responses to questions 5 and 6 (see CTP Section 10.3 for questionnaire) will be made consistent to the extent that if the answer to question 5 is 5 (none of the time) and the answer to question 6 is non-missing (i.e., length of worst attack specified), then question 6 will be set to missing. Therefore scores will be calculated ignoring that item. In this case, the missing response to question 6 will not be included in the count of missing questions for the symptoms component.

6.6.2.2 University of California, San Diego Shortness-of-Breath Questionnaire

If UCSD-SOBQ is not completely answered, the missing questions will not be imputed and the score will be set to missing.

6.6.2.3 King's Brief ILD Questionnaire

For K-BILD, missing item scores are imputed based on the average of the non-missing item scores within the domain, rounded to the nearest integer. If the missing items are >50% per domain, then the domain score is set to missing. If item 15 is missing, it will be replaced by the average of all available items 1-14. If any of the domain scores are missing, the total score is set to missing.

6.6.3 Other Endpoints

6.6.3.1 Concomitant therapies

In case of (partially) missing start and end dates of concomitant therapies, the dates will be imputed so that the extent of exposure to the concomitant therapy is maximal, i.e. the first day (month) of the month (year) for incomplete start dates and the last day (month) of the month (year) for incomplete end dates.

6.6.3.2 Safety Endpoints

Information regarding acute IPF exacerbations is collected from AEs and as such, missing or incomplete start or end dates will be imputed according to BI standards (1).

6.7 BASELINE, TIME WINDOWS AND CALCULATED VISITS

As a general rule, last assessment before treatment period start (included) will be used as baseline. For patients randomized to the Non-Pulmonary Rehabilitation group treatment period starts from randomization. For patients randomized to the Pulmonary Rehabilitation group treatment period starts from first day of pulmonary rehabilitation. If the baseline value is missing and the screening value is available, then the baseline value will be defined as the screening value taken closest to baseline date.

A windowing will be performed in order to assign data to the relevant study visit based on the actual day of the assessment. If after windowing of visits at baseline, two values fall within the same baseline interval, then the last value will be taken into account. If after windowing of

post-baseline visits, two visits fall in the same interval, then the measurement closest to the planned visit will be taken into account. In case two measurements are equidistant from the planned visit, then the last one will be picked.

Time windowing rules for physical exam, vital signs, and laboratory tests:

Time window of actual day			Allocated to		
Start day	End day (included)	Length of the time-window [days]	Visit number	Visit name	Planned day of the visit
-	1	-	2	Baseline	1
2	32	31	3	3 weeks	22
33	63	31	4	6 weeks	43
64	105	42	5	12 weeks	85
106	147	42	6	18 weeks	127
148	-	-	7	24 weeks	169

Time windowing rules for spirometry, six minutes walk test, [REDACTED], PROactive tool, SGRQ, KBILD, UCSD SOBQ:

Time window of actual day			Allocated to		
Start day	End day (included)	Length of the time-window [days]	Visit number	Visit name	Planned day of the visit
-	1	-	2	Baseline	1
2	126	125	5	12 weeks	85
127	-	-	7	24 weeks	169

Include for analysis and in average calculation of the ProActive tool scores the following measurements. If a patient does not have at least 5 days of measurements available, no score is calculated (except for baseline, noted below).

- Baseline = 7 days before and up to actual Visit 2 (excluded). If a patient does not have at least 5 days of measurements within this time window, then use 7 days before and up to actual Visit 1 (excluded) (only if 5 days of measurements are available)
- 12 weeks = 7 days before and up to actual Visit 5 (excluded)
- 24 weeks = 7 days before and up to actual Visit 12 (excluded)

Note: For accelerometer scores, if a patient has more than one record for a given day, the record will not be used for calculation. For eDiary scores, if a patient has more than one record for a given day, the worse answer will be used for calculation.

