5.1.2 Assessment of efficacy

5.1.2.1 6 Minute walk test

The distance measured in the 6 Minute Walk Test at 12 and 24 weeks will be assessed according to the procedures described in [Appendix 10.1](#).

Four 6 MWTs will be performed during the trial (one practice and three tests). At Visit 1 a practice 6 MWT, also referred to as the Titration Walk Test, will be conducted to acquaint the patient with the procedure and to determine the level of oxygen needed for subsequent testing. As per inclusion criterion #8, patients must be physically able to perform a 6MWT, as per the instructions. Patients who cannot complete the Titration Walk Test will be considered a Screen Failure. Three 6 MWTs will be conducted during the randomized treatment phase at Visits 2 (baseline), 5 and 7 (End of Treatment). During the 6 MWT, the Borg Scale will be administered. Detailed instructions for the conduct of the 6 MWT and Borg Scale are provided in the ISF and Appendix 10.1 and [10.2](#) and in the distributed instructional video. It is important the instructions are followed exactly. The test will be performed at approximately the same time each day from time of Visit 2 testing. Patients who cannot complete the 6MWT after randomization will remain in the trial.

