6. INVESTIGATIONAL PLAN

6.1 VISIT SCHEDULE

This trial consists of two parts, a screening and an interventional period. The screening period consists of the time between signing consent and randomization, and will last a minimum of 7 days. The interventional period consists of the time from randomization through the week 24 assessment visit.

There are two screening visits (Visit 1, which must be preceded by a separate informed consent Visit 0) and 6 visits (Visits 2 to 7) planned within the 24 week interventional period. There is no follow up period in this trial.

After giving his/her informed consent, the patient will be screened for inclusion (see [Section 3.3.2](#) and exclusion criteria (see [Section 3.3.3](#)) for the trial at Visits 0, 1 and Visit 2 (refer to [Flowchart](#)).

The patient will be dispensed an activity monitor and ProActive tool (eDiary) at the consent visit, and will wear the activity monitor and use the eDiary for 7 days prior to Visit 1 for training purposes.

Visit 2 can be performed once the results from local laboratory of Visit 1 are obtained and the patient has worn the activity monitor and completed the eDiary for 7 days. If for any reason the screening phase for an individual patient lasts for more than 6 weeks, then the laboratory examination for Visit 1 has to be repeated before randomization. The patient will be randomized at Visit 2 if all inclusion and none of the exclusion criteria are fulfilled. Central HCRT is not required prior to randomization, but if historical HRCT is not available to be sent for central calculation of QLF, a scan should be obtained after screening/consent at the latest 7 days after Visit 2.

On treatment visits will be performed at 3, 6, 12, 18 and 24 weeks. Procedures for these visits are outlined in the flow chart and detailed instructions are available in [Section 5](#), select appendices and the ISF, as applicable.

Visit 7 is the end of treatment visit, there is no follow up period. Visit 7 procedures should be followed for early termination visits if possible.

If a patient misses a visit, the visit should be rescheduled as soon as possible. If unable to reschedule, the clinical monitor should be contacted.

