Distractions: During the exercise tests, access to the laboratory should be restricted to trial staff as much as possible. The noise level in the laboratory should be kept to a minimum, except for those sounds specifically related to the conduct of the test. This will ensure that the subject is able to concentrate on the task at hand, and will also ensure that the subject is attentive to the verbal encouragement provided by the designated member of the trial team.

Comfort with equipment: Subjects should be appropriately dressed for exercise (e.g., shorts or track pants, gym shoes, T-shirt or sweat shirt), and trial staff should ensure that the subject is comfortable with the equipment prior to starting the exercise.

Familiarity with test: Before starting exercise, a member of the trial team should make sure that the subject is completely familiar with the type of exercise that is to be performed, a practice test is expected prior to the baseline test at Visit 2 to allow patients to become familiar with the testing procedures.

Performance incentives: No external incentives for performance (i.e., rewards for performance) should be given to the subject, prior to or at any time during the exercise.

Personnel qualifications:

Exercise challenges should be conducted by adequately trained personnel with a basic knowledge of exercise physiology.

Technicians familiar with normal and abnormal responses during exercise and trained in CPR should be present throughout the tests.

Safety issues:

Cardiac (bradyarrhythmias, ventricular tachycardia, myocardial infarction, heart failure, hypotension, and shock) and non-cardiac (musculoskeletal trauma, severe fatigue, dizziness, fainting, body aches) complications of exercise challenges have been reported.

Consequently during the test, study personnel should be alert to any abnormal event. Indications to stop the test must be clearly established and known by the personnel involved in testing.

Symptoms such as:

- acute chest pain,
- sudden pallor,
- loss of co-ordination,
- mental confusion,
- extreme dyspnoea.

If the exercise test has been stopped for one of these reasons, the subject should be monitored in the laboratory until signs / symptoms / ECG modifications have completely cleared. Full CPR equipment should be available in the laboratory. Further participation in any exercise testing and continuation of the patient in the study should be discussed with the clinical monitor.

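### As written, SAP 6.7 lets the practice/oxygen-titration walk stand in for a missing 6MWD baseline, and a training week for a short activity baseline, against the protocol's Day 1 baseline and deviation E2

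*SAP*

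**What the plan says.** **Baseline rule.** SAP 6.7 takes the last assessment up to the start of the treatment period as baseline. If that is missing and a screening value is available, "then the baseline value will be defined as the screening value taken closest to baseline date". No endpoint is excepted. The baseline window for the walk test ends on Day 1 and has no start day, so a Visit 1 walk also falls inside it.

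**The Visit 1 walk.** Protocol 5.1.2.1 plans one practice walk and three tests, and names Visit 2 as baseline. The practice walk, held at Visit 1, doubles as the titration walk. Its stated purpose is "to acquaint the patient with the procedure and to determine the level of oxygen needed for subsequent testing". Protocol 10.1.1 lists the practice walk among its measures against variable exercise performance: "a practice test is expected prior to the baseline test at Visit 2 to allow patients to become familiar with the testing procedures".

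**Activity.** Protocol 6.1 says that the patient "will wear the activity monitor and use the eDiary for 7 days prior to Visit 1 for training purposes". SAP 6.7 uses that same week as the PROactive baseline when the week before Visit 2 has fewer than 5 days of measurements, provided the earlier week has 5.

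**Missing data.** Protocol 7.3.1 takes the baseline of the primary model from Day 1 of the interventional period. Protocol 7.5 rules out imputation for continuous efficacy endpoints, apart from a sensitivity analysis. SAP 6.6 describes the analyses, in general, as "using only available data without imputation". SAP 5.2.2 sends the reader to 6.6 for a missing baseline, but the substitution rule is in 6.7. SAP 6.2 lists a missing baseline 6MWD as important deviation E2 and excludes nobody on that ground.

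**The concern.** The protocol places a practice walk and a practice monitoring week ahead of baseline so that patients know the procedures by the time baseline is taken. The SAP fallback can bring those same measurements back as the baseline. For an affected patient, the 6MWD change would then run from a familiarisation and titration walk to a test done after the oxygen level was set. It would not run from one scheduled test to another.

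The rule also leaves the handling of a missing Visit 2 walk undefined. The SAP does not say whether the practice distance counts as a screening value, whether such a patient is reported under E2, or whether a change score is still produced. After termination, SAP 4 limits the primary and secondary endpoints to descriptive results. Change from baseline by arm is therefore what will be reported, and the multiple-imputation sensitivity analysis in SAP 7.4.2 is struck out.

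**Working it through.** **1. Is there always a fallback value for 6MWD?** Inclusion criterion 8 (Protocol 3.3.2) requires successful completion of the practice walk. Protocol 5.1.2.1 makes a patient who cannot complete it a screen failure. Every eligible randomised patient should therefore have a Visit 1 walk.

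**2. What does that do to E2?** There are two ways to program it.
- On the derived baseline: the practice walk fills every gap, so E2 almost never fires.
- On the Visit 2 walk: E2 flags the patient as having no baseline, while a change from baseline is still reported.

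The SAP does not say which applies. SAP 4 records E2 as a deliberate addition, so neither result looks intended.

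**3. The plan's own yardstick.** Protocol 7.7 uses a 30 m difference, SD 85 m, 80% power and two-sided alpha 0.05. Per arm, n = 2 × (1.960 + 0.842)² × 85² / 30² = 126.02, rounded up to 127, or 254 in total. This matches the stated 254, and the exact t calculation also gives 127 per arm (power 80.0%). The point does not depend on the sample size; 30 m serves only as a scale.

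**4. Size of the effect on 6MWD.** Let f be the share of an arm with a filled baseline, and L the mean of the Visit 2 distance minus the practice distance. The documents give neither, so both are assumptions. The sign of L is also assumed; if L is negative, every shift below reverses.

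Shift in an arm's mean change = f × L:

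| f | Patients per 145 | L = 10 m | L = 20 m | L = 30 m |
|---|---|---|---|---|
| 2% | 2.9 | 0.2 m | 0.4 m | 0.6 m |
| 5% | 7.25 | 0.5 m | 1.0 m | 1.5 m |
| 10% | 14.5 | 1.0 m | 2.0 m | 3.0 m |

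The 145 is the planned number per arm; the number reached before termination is not given. At the planning figures, the standard error of an arm mean is 85/√127 = 7.5 m.

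Shift in the unadjusted between-arm difference = (f1 − f0) × L, with the same L in both arms:
- 5% v 5%: 0 m.
- 10% v 5%: 0.05 × 10 = 0.5 m to 0.05 × 30 = 1.5 m.
- 10% v 0%: 0.10 × 10 = 1.0 m to 0.10 × 30 = 3.0 m, at most 3.0/30 = 10% of the target difference.

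With 6MWD taken out of the fallback, this contribution is 0 and the affected patients have no change score.

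**5. Activity.** No figure can be attached. The documents give no size or direction for a training effect and no rate of short Visit 2 weeks.

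**The case against.** The strongest reply has four parts.

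**The SAP may not mean the practice walk.** The protocol separates it from the three tests, and E2 suggests that the authors expected some patients to have no baseline 6MWD. This is fair, but it shows an ambiguity rather than a safeguard: nothing in SAP 6.7 removes the practice walk, and its open-ended window admits it.

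**An earlier observed value is not imputation.** SAP 6.6 speaks only in general terms, and using a real measurement from the same patient can be read as defining baseline. If so, the tension with SAP 6.6 and Protocol 7.5 weakens, but the definition still differs from the Day 1 baseline of Protocol 7.3.1.

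**The activity fallback is explicit and reasonable.** It needs the same 5 days, and flow-chart footnote 2 describes the weeks before Visits 1, 2, 5 and 7 alike. This stands. Dropping the fallback would exchange a similar pre-treatment week for lost patients.

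**Little depends on it.** Visit 2 is the randomisation visit, and Protocol 10.1.2 records the distance even of a walk stopped early, so missing distances should be rare. No test is left to distort. This also stands, and it limits the weight of the point.

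A reader might go further and infer that learning is being counted as improvement in both arms. The documents do not support that. They do not say that the practice walk is a patient's first ever, they leave the titration procedure to site instructions, and they give no direction for a practice, oxygen or training effect. An assumed gain of 10–30 m is 33–100% of 30 m for one patient, but that says nothing about a reported mean.

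**Conclusion.** The point holds as a defect in the baseline definition, of minor weight. SAP 6.7 as written admits the practice walk as a 6MWD baseline, departs from Protocol 7.3.1 and 7.5, and cannot be squared with E2. For activity it uses as baseline a week that the protocol describes as training. That choice should be made visible; it is not shown to be wrong.

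The effect on arm means is probably small: 0.2–1.5 m for 2–5% filled baselines and an assumed 10–30 m gain, and up to 3.0 m at 10%. A biased treatment comparison is a further inference that the documents do not establish, since balanced missingness gives no shift. Balance is not assured: the trial is open label, and the Visit 2 list in Protocol 6.2.2 puts randomisation before the walk, although the order may be adapted. The analysis is now descriptive, so no hypothesis test is affected.

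**What to change.** - **6MWD.** In SAP 6.7, exclude 6MWD from the screening fallback. A missing Visit 2 walk then means a missing 6MWD baseline, the patient is counted under E2, and no change score is calculated.
- **Cross-reference.** In SAP 5.2.2, point to 6.7 instead of 6.6 for a missing baseline.
- **Steps, VMU and PROactive scores.** Keep the fallback, but report the number of filled baselines by arm and the results with and without them.
- **Spirometry and questionnaires.** No change is needed; the flow chart schedules them at Visits 1 and 2 without a practice label.

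The cost is a few sentences, a small programming change and slightly more tabulation. A few patients would leave the 6MWD change-from-baseline tables.

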7.3.1 Primary endpoint analyses

The primary analysis is a restricted maximum likelihood (REML) based analysis of covariance (ANCOVA) comparing the change from baseline of 6MWD after 12 weeks of treatment with adjustment for the covariates of intervention as a fixed categorical covariate and baseline 6MWD value as a continuous covariate.

The statistical model will be as follows:

$$y_{ij} = \beta S_i + \tau_j + e_i$$

y_{ij} = response variable for the subject i receiving intervention j

β = fixed effect regression coefficient of baseline effect

S_i = the baseline measurement of subject i , $i = 1, 2, \dots$ where the baseline measurement is collected on Day 1 of the interventional period

τ_j = the fixed effect of intervention j , $j = 1, 2$

e_i = the random error associated with the i^{th} subject, identically independent normally distributed with mean 0 and unknown variance σ^2 .

The Kenward-Roger approximation will be used to estimate denominator degrees of freedom and adjust standard errors. Significance tests will be based on least-squares means using a two-sided $\alpha = 0.05$ (two-sided 95% confidence intervals). The primary intervention comparison will be the least-squares means contrast between interventions. Primary endpoint analyses will be done on complete cases. Section 7.3.2 discusses planned sensitivity analysis to assess the impact of patients missing post-randomisation data.

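### The SAP's 12-week efficacy window opens at day 2, so a lone early-termination walk, spirometry or questionnaire value is summarised as the week-12 value

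*SAP*

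**What the plan says.** SAP 6.7 assigns data to visits by calendar day: "A windowing will be performed in order to assign data to the relevant study visit based on the actual day of the assessment". It has two tables. For spirometry, the six-minute walk, SGRQ, KBILD and UCSD-SOBQ, the 12-week row reads "2 126 125 5 12 weeks 85" (start day, end day, length, visit number, visit name, planned day). Everything from day 127 goes to 24 weeks. The other table, for physical examination, vital signs and laboratory tests, gives days 2 to 32 to 3 weeks, 33 to 63 to 6 weeks and 64 to 105 to 12 weeks. The PROactive tool is listed with the efficacy measures but has its own rule, the seven days before the actual visit, so it is left aside here.

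If "two visits fall in the same interval, then the measurement closest to the planned visit will be taken into account". Nothing is said about a single value far from the planned day.

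On exit assessments, Protocol 6.1 says "Visit 7 procedures should be followed for early termination visits if possible". The Visit 7 list in Protocol 6.2.3, which applies also at discontinuation, includes the walk, spirometry and the questionnaires.

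On the endpoint, Protocol 7.3.1 describes the primary analysis as "comparing the change from baseline of 6MWD after 12 weeks of treatment", on complete cases. SAP 6.6 uses available data without imputation. SAP 6.2 excludes no patient for a deviation. SAP 4 and 7.4.1 now limit the primary endpoint to descriptive statistics.

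**The concern.** The protocol produces early walks, and the SAP gives them the week-12 label. A patient who leaves on day 10 and has an exit walk enters the primary summary beside patients who had 12 weeks of follow-up. In the rehabilitation arm that walk follows little of the programme, or none of it if days are counted from randomisation and the patient never started.

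This conflicts with the endpoint as change after 12 weeks of treatment. It also works much like carrying an early value forward, although SAP 6.6 promises no imputation. The same exit visit would be called 3 weeks for vital signs and 12 weeks for the walk.

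What is at stake is the reported week-12 result in each arm. N would count some non-completers as week-12 cases, and the mean and SD would mix week-12 values with earlier ones.

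**Working it through.** **1. The plan's own window figures.** Length: 126 − 2 + 1 = 125 days, as SAP 6.7 states. The 24-week window starts at the midpoint of the two planned days: (85 + 169)/2 = 127. The upper bound therefore follows a midpoint rule. The lower bound does not: the midpoint of days 1 and 85 is (1 + 85)/2 = 43, but the window opens at day 2.

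**2. Reach.** Before the planned day: 85 − 2 = 83 days. After it: 126 − 85 = 41 days. The flow chart allows ±3 days for Visit 5, that is days 82 to 88.

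**3. A lone exit assessment under each table of SAP 6.7.**

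| Day | Efficacy table | Other table |
|---|---|---|
| 10 | 12 weeks | 3 weeks |
| 22 | 12 weeks | 3 weeks |
| 43 | 12 weeks | 6 weeks |
| 63 | 12 weeks | 6 weeks |
| 64 | 12 weeks | 12 weeks |

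**4. Programme received.** Protocol 4.1.1 plans two or three sessions a week for 12 weeks, so 24 to 36 sessions. With day 1 as the first session, day 43 is 6 weeks in (12 to 18 planned sessions) and day 64 is 9 weeks in (18 to 27). Day 10 is 9 days in, little over one week.

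**5. Illustration of size (assumed, not a bound).** Let *f* be the share of an arm's week-12 values that are early exit walks, *m* the mean change of the others and *x* the mean change of the exit walks. The reported mean is (1 − *f*)·*m* + *f*·*x*. With a common SD of 85.0 m (Protocol 7.7), the reported SD is √(85² + *f*(1 − *f*)(*m* − *x*)²). Take *f* = 10%, borrowed from the planning drop-out in Protocol 7.7, and *m* = 30 m:

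- *x* = 30: mean 30.0, SD 85.0
- *x* = 15: mean 0.9 × 30 + 0.1 × 15 = 28.5
- *x* = 0: mean 27.0, SD √(7225 + 0.09 × 900) = 85.5
- *x* = −30: mean 27.0 − 3.0 = 24.0, SD √(7225 + 0.09 × 3600) = 86.9

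At *f* = 5% and *x* = 0 the mean is 28.5. For N, 10% of the planned 141 per arm is about 14, so 141 would be shown where 127 have a walk near week 12. Enrolment at termination is not given.

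**6. Day 1.** SAP 6.7 makes baseline the last assessment up to and including treatment start, ends the baseline window at day 1, and says "For patients randomized to the Pulmonary Rehabilitation group treatment period starts from first day of pulmonary rehabilitation". These agree only if day 1 is treatment start. Flow-chart footnote 6 likewise moves all visits with the first session. Against this, Protocol 7.3.1 speaks of a baseline "where the baseline measurement is collected on Day 1 of the interventional period", Protocol 6.1 says "The interventional period consists of the time from randomization through the week 24 assessment visit", and Protocol 6.2.2 begins the treatment phase at Visit 2.

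Counted from the first session, no on-schedule visit is misallocated. Counted from randomisation with a delay of *D* days, Visit 5 falls on day 85 + *D*. It reaches day 127, and the 24-week label, only at *D* = 42, or from *D* = 39 if Visit 5 is 3 days late. If the six weeks in Protocol 6.2.2 are the whole gap between Visits 2 and 3, the extra delay is 42 − 21 = 21 days and Visit 5 falls on day 106, inside the window.

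**The case against.** The strongest defence is that inclusive use of data is deliberate. Protocol 7.3 uses all measurements from Visits 2 to 7, SAP 6.1 covers both the post-randomisation and treatment periods, and the Randomized Set includes patients whether or not they had rehabilitation. Using a measurement, however, does not require calling it week 12. A separate row uses it just as fully.

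Other context reduces the harm. Exit walks happen only if possible and with the patient's agreement, and none follows withdrawal of consent. The SAP also reports deviations (including rehabilitation compliance below 80%), duration of rehabilitation and disposition. This stands, but none of it shows which week-12 values are early.

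Two objections limit the point. First, day 64 comes from a schedule with a week-6 visit, whereas no walk is planned at week 6. It is a convenient bound rather than a necessary one, and day 43 fits the efficacy table's own midpoint logic better. Second, a reader might infer that the SAP leaves day 1 undefined and so loses delayed Visit 5 walks. The documents do not support that: SAP 6.7 and footnote 6 point to treatment start, and the loss needs both the randomisation anchor and a delay of about 39 to 42 days.

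**Conclusion.** The point holds for the window. As written, SAP 6.7 reports a lone post-baseline value from any day between 2 and 126 as the week-12 value, and no other rule in the plan prevents it. This is firm for controls and for rehabilitation patients who have started. For those who never start, it depends on an anchor that the SAP does not give.

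The effect is confined to the descriptive week-12 summaries by arm. A reader might infer a diluted treatment effect, a bias against rehabilitation or a compromised test. None of these follows: no between-arm contrast or test is now planned, and the sign depends on how exit walks compare with the other walks and on which arm they come from. Nor is 10% an upper limit. It is a planning assumption, the trial was terminated, and the documents do not say how many patients left early or had an exit walk.

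The anchor is a secondary clarification. Treatment start is implied but not stated, some protocol wording points to randomisation, and a rehabilitation patient who never starts has no day 1.

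**What to change.** In the efficacy table of SAP 6.7, start the 12-week window at day 43 (midpoint of days 1 and 85, matching how day 127 is set) or at day 64 (the SAP's own bound in its other table). Keep day 126 as the end. Show earlier post-baseline values in a separate early-termination row by arm, with their own N, mean and SD. If deviation E1 (no walk at 12 weeks) is programmed on windowed visits, which the SAP does not say, evaluate it on the same window.

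Add one sentence stating from which day the actual day is counted in each arm, and which day applies to rehabilitation patients who never start.

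The cost is one number in one table, one summary row and a sentence or two. With days counted from treatment start, no on-schedule Visit 5 walk is lost, since days 82 to 88 lie inside either window. There are two downsides. A few values leave the week-12 summary, which can itself shift the mean, so both rows should be shown. A lone exit walk after the new bound still counts as week 12; the later start, day 64, leaves fewer of these but moves more values out.
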